It was observed that the home visit component of the NET-Works intervention was delivered to N=257 out of N=265 intervention group families by 7 family connectors. Because it is possible that characteristics of particular FCs may be related to BMI outcomes of the families to which they are assigned, we determined that it would be prudent to model this potential source of dependency in the primary outcome.
The decision to omit the random ECFE term and estimate a random FC term was made after study recruitment was complete and sample size was therefore fixed.
- Family Connector specification
The method for coding the Family Connector was not previously specified. Seven FCs delivered the home visit intervention component to 257 of the 265 treatment group families. Each of these 257 families will be assigned to a FC group based on the primary FC with whom they worked. Treatment group families that did not participate in the home visit intervention component, and all control group families, will be assigned to their own n=1 FC group.
- Multiple imputation specifications
We indicated previously that variables from the analytic model as well as auxiliary variables and interactions would be used in the imputation model. We have now specified a list of 9 candidate auxiliary variables and decided not to include interactions. We also provide more specificity regarding the number of datasets to be imputed (minimum 20) and the principles guiding decisions about the imputation process.

B2: Revised Analysis Plan

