2.1. Study Design

The study is an individually randomized group trial. Families will be randomized equally to the NET-Works intervention or a control group. The NET-Works intervention duration is thirty-six months. Outcome measures will be assessed at baseline and at 12, 24 and 36 months post-randomization.

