2.4. Primary Analysis

2.4.1. Statistical model and approach

The primary analysis will test whether NET-Works participants have lower BMI at 24 and 36 months relative to comparison participants. We will use data from all randomized participants (intent to treat approach) to estimate two mixed models in which 24 or 36 month BMI values are predicted from randomized treatment group with age group at baseline, sex and BMI at baseline as covariates, and a random intercept for family connector (u_{0j}):

$$\text{BMI}_{ij} = \gamma_{00} + \gamma_{01}\text{NET-Works}_j + \gamma_{20}\text{3yo}_i + \gamma_{30}\text{4yo}_i + \gamma_{40}\text{female}_i + \gamma_{50}\text{BMI baseline}_i + [u_{0j} + e_{ij}].$$

We will conclude that NET-Works was efficacious if the γ_{01} parameter in both mixed models is statistically significant and negative, meaning that BMI is significantly lower among NET-Works children than comparison children.

[figure not shown]
A source of dependence lies in the family connector (FC) assignment. Seven family connectors delivered the home visit component of NET-Works to intervention families. To the extent FC assignments were intended to be culture-specific, and FCs may vary slightly in their manner of delivering intervention content to the families with whom they work, dependence may be introduced through common FC assignment. As such, it will be important to account for dependence in BMI introduced through FC assignment.

Each of the families will be assigned to a FC group based on the primary FC with whom they worked. Treatment group families that did not participate in the home visit intervention component, and all control group families, will be assigned to their own n=1 FC group following the method of Esserman et al. (2012).

2.4.3. Missing data including level of attrition, loss to follow-up, and missing data treatment

The primary analysis will be conducted using multiply imputed data. We plan to use fully conditional specification to impute sporadically missing followed by 12, 24 and 36 month monotonically missing BMI values. We anticipate imputing a minimum of 20 datasets based on the observed missingness to date in post-baseline BMI values but may upwardly adjust this number to ensure adequate power (Graham et al., 2007). The imputation model will include the

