2.10. Statistical analyses

2.10.1. Primary analyses

The primary efficacy analysis will test whether income racial/ethnic minority of two to four year old children who are randomized to the NET-Works program have statistically and clinically lower BMI at 24 and 36 months post-randomization relative to usual care comparison group children. Data from all randomized participants will be used to estimate two mixed models. In each, BMI at either 24 or 36 months will be predicted from treatment group (NET-Works, usual care) with age at randomization (2, 3, 4), sex (F, M) and BMI at baseline included as covariates. The NET-Works study is an individually randomized group trial, and dependence may be introduced into the BMI values of NET-Works children whose parents participate in common parenting classes over the course of the three-year intervention while there is unlikely to be dependence in the usual care group where parents are unlikely to ever interact with each other [49]. Among NET-Works children randomized to the intervention group, parenting class cohort will be treated as a random effect, and the intraclass correlation of BMI among children within cohorts will be estimated. Each usual care child will be treated as a random effect and BMI assumed independent. It will be concluded that NET-Works was efficacious if the fixed treatment group parameter in both mixed models is statistically significant and BMI is meaningfully lower (Cohen's $d \geq .30$) among NET-Works children.

Table 2

NET-Works process evaluation.

Fidelity. The extent to which the intervention is delivered as intended; quality of the intervention; how well an intervention is being implemented compared to its original design; could include, but not limited to, content & quality of messages, adherence to protocol, and intervention staff skill/training/certification.

Intervention component	Construct(s)	Data collection method	Completed by	Timing of data collection
Primary care	Content of messages received	Adherence survey	Parent	Baseline, 6, 12, 18, 24, 30 and 36 months
	Provider training attendance and satisfaction	Survey	Pediatric primary care providers	After provider training
Home visits and check-in calls	Content and quality of messages delivered/received	Documentation forms	Intervention staff	After every visit/call
	Staff training attendance, certification and satisfaction	Satisfaction survey	Parent	6, 18, and 30 months

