2.10.2. Detectable difference, sample size and power

A power analysis determined the minimum detectable standardized effect size (MDSE, Cohen's d) in BMI for NET-Works versus usual care children at 24 or 36 months post-randomization (i.e., the fixed treatment group parameter). The effective number of follow-up BMI observations was estimated separately for each treatment group by imposing assumptions about the design effect resulting from NET-Works parent-child dyads clustered within parenting class cohorts ($ICC_{PC} = .01\text{--}.03$ NET-Works, $ICC_{PC} = .00$ usual care), the design effect resulting from autocorrelation within cohorts ($r_{PC} = .30\text{--}.50$ NET-Works, $r_{PC} = .00$ usual care) and children ($r_{child} = .40\text{--}.60$) between baseline and follow-up BMI, and the proportion of children from whom BMI will be available (75–85%) (Table 3).

NET-Works dyads will be clustered within about 16 parenting class cohorts ($M = 15.6$ dyads/cohort). The clustered sample size in each treatment group ($n = 250$) was divided by the design effect introduced by clustering within parenting classes, $DEFF_{PC} = [1 + (n - 1)\rho]$, to estimate the effective number of independent dyads in each group. Next, the effective number of independent dyads was divided by the design effect introduced by cohort and child autocorrelation in BMI, $DEFF_{corr} = (1 - r^2)$, to adjust for the efficiency gain resulting from controlling for baseline BMI. In this case, $r = [np/(1 + (n - 1)\rho)]\rho_c + [(1 - \rho)/(1 + (n - 1)\rho)]\rho_s$, where n is the average number of dyads per cluster; ρ is the correlation in BMI values of different children in the same cluster at a single point in time, ICC_{PC} ; ρ_c is the cohort auto-correlation in BMI values, r_{PC} ; and ρ_s is the child auto-correlation in BMI values, r_{child} [51,52]. Finally, the NET-Works and usual care sample sizes were reduced to 75–85% of their estimated values to account for the expected number of children with a follow-up BMI. We will use a generalized Holm procedure to ensure a family-wise Type I error rate of .05 in the two mixed models, so that the treatment group parameter with the smaller p-value will be tested at $\alpha_2 = .025$, while the treatment group parameter with the larger p-value will be tested at $\alpha_2 = .05$ [53,54].

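### The primary model holds both arms to one total residual variance, so any difference in spread between arms is absorbed into the family connector variance and can cost power

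*Protocol*

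**What the plan says.** The revised analysis plan (part B2, section 2.4.1) specifies two mixed models, for BMI at 24 and at 36 months. Each has treatment, age group, sex and baseline BMI as fixed effects. The random part of the equation is a single connector intercept u plus a single residual e, and neither variance is indexed by arm.

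On coding, the section says that unvisited intervention families and "all control group families, will be assigned to their own n=1 FC group". The summary of adjustments (part A2) gives the same rule and the cluster structure: "Seven FCs delivered the home visit intervention component to 257 of the 265 treatment group families". That leaves eight intervention families as singletons.

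On allocation, section 2.1 of the revised plan says: "Families will be randomized equally to the NET-Works intervention or a control group". The control count does not appear in the text.

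Efficacy is claimed only if the treatment coefficient is negative and significant in both models.

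**The concern.** Control families have no connector. As singletons they nevertheless carry Var(u) + Var(e), and because the equation has only one of each variance, the control arm is held to the intervention arm's total.

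Var(e) is estimated mainly from differences between families who share a connector. The sum Var(u) + Var(e) is estimated mainly from the singletons, which are nearly all controls. A gap between control spread and within-connector spread is therefore assigned to Var(u). The seven connector means carry little information with which to resist it.

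Var(u) drives the standard error of the treatment effect. If controls are more variable, Var(u) is inflated and power is lost. If they are less variable, Var(u) is understated and the test becomes somewhat liberal. Since both models must be significant, a loss of power at either time point can defeat a true effect.

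**Working it through.** **The plan's own figure.** The design paper (section 2.10.2) gives a minimum detectable effect of .305 at ICC .02, 80% follow-up and two-sided alpha .025. Power is not stated; I took 80%.
- Clustering: 1 + (15.6 − 1)(.02) = 1.292.
- r = (15.6 × .02/1.292)(.30) + (.98/1.292)(.40) = .376, and 1 − r² = .859.
- Intervention effective n: 250/1.292/.859 × .80 = 180. Control: 250/.84 × .80 = 238.
- (2.241 + .842) × √(1/180 + 1/238) = .304, or .305 with t quantiles. At alpha .05 the result is .277, as stated.

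So the published figure reproduces. It treats the two arms as equally variable and does not test that assumption.

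**Inputs for the check.**
- From the Protocol: 7 connectors, 257 visited families (about 37 each), 8 intervention singletons, ICC range .01–.03, r_child = .40, d = .30.
- Assumed: 265 controls (from equal allocation), equal caseloads, complete outcomes, and the variance ratios. The ICC range was stated for parenting classes; applying it to connectors is also an assumption.
- Scale: total baseline-adjusted variance is 1 in the intervention arm and VR in the control arm. The effect is .30/√(1 − .40²) = .327 residual SD.

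**Mechanism at VR = 1.33, ICC .02.** Within-connector variance is .98 and singleton control variance is 1.33, so the controls alone would put Var(u) near 1.33 − .98 = .35. The connector means point to .02. The REML compromise averages an estimated ICC of about .10.

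**Hand check of the consequence.**
- True sampling variance of the effect: .02/7 + .98/257 + 1.33/265 = .0029 + .0038 + .0050 = .0117, so SE = .108. Power by z: Φ(.327/.108 − 1.96) ≈ .86.
- With Var(u) taken as roughly .10, the first term becomes .10/7 = .0143, the sum .0231 and the reported SE .152. The critical difference is 1.96 × .152 = .298. Power is then Φ((.327 − .298)/.108) ≈ .61.

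This uses the average estimate only; simulation, which lets the estimate vary, gives .67.

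**Simulation.** REML, 10,000 trials per cell, ICC .02, two-sided .05 in one model. Entries are Wald z / Satterthwaite.

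| VR | Mean estimated ICC, as planned | Power as planned | Power arm-specific | Loss (points) |
|---|---|---|---|---|
| 1 | .023 | .887 / .863 | .890 / .862 | 0 |
| 1.1 | .032 | .856 / .823 | .883 / .851 | 3 / 3 |
| 1.33 | .096 | .668 / .636 | .860 / .830 | 19 / 19 |

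Smaller simulations, by z or residual degrees of freedom:
- VR = 1.33: 73% against 86%, and 65% against 79% (13 and 14 points).
- VR = 1.18: 79% against 84% (5 points).

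A further one, with 212 followed families per arm, put the larger variance at 1 and the smaller at .85 or .75:
- 1/.85 = 1.18: 82% against 87% (residual df), 75% against 84% (Satterthwaite).
- 1/.75 = 1.33: 73% against 89%, and 63% against 87%. The last gap, 24 points, is the largest seen at ICC .02.

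Across the plan's ICC range, the 10,000-trial loss at VR = 1.33 is 15 to 16 points at ICC .01 (.737 / .710 against .891 / .870) and 23 at ICC .03 (.602 / .563 against .828 / .790).

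**Type I error, planned model, ICC .02.** At VR = 1 it is .060 / .049; at VR = .75 it is .066 / .054. Unequal spread adds .066 − .060 = .006 by z and .054 − .049 = .005 with Satterthwaite. The rest of the excess in the z figure comes from having few clusters. At VR = 1.33 the test is conservative, .041 / .036. The arm-specific model with Satterthwaite stays at .046–.052 for VR from 0.5 to 2.

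**The case against.** **The coding is not the cause by itself.** True. Singleton groups combined with a separate residual variance per arm would not force a common total. The constraint comes from the coding together with a single u variance and a single e variance. The plan states no residual distribution, and covariance structure is often left to the SAP or the code. Still, this document presents itself as the final revised analysis plan, and its equation indexes neither variance by arm, so the common-variance reading is the natural one. If the rehearsed code already allows variance to differ by arm, the point reduces to saying so. The coding follows a cited methods paper, which was not available; citing it does not remove the constraint.

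**Unequal spread has not been shown.** This stands. A reader might infer it from eligibility with no upper BMI limit, reasoning that the programme restrains the heaviest children most. The documents do not support that step, because baseline BMI is a covariate. In a check with 200,000 children per arm and effects that grow with baseline BMI, raw control-to-intervention variance ratios reached 1.07–1.74 while baseline-adjusted ratios stayed at .99–1.01. Only a difference in spread unrelated to baseline BMI matters here.

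**A reader might also infer that the planned test is seriously anti-conservative.** It is not, at ratios near 1 and ICCs in the plan's range. Ratios of 0.9 to 1.1 move type I error by about .01 or less, and at ICC 0 lower control spread causes no inflation. The requirement that both models be significant can only lower the chance of a false claim.

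**The change may reach into the imputation.** This also stands. An imputation model with one residual variance would pull the arms' variances together among imputed values, and the simulations used complete outcomes.

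**Conclusion.** The point holds as a modelling weakness whose main consequence is lost power when controls are more variable than intervention children after adjustment for baseline. At ICC .02 and d = .30 the loss is about 3 points at a variance ratio of 1.1, about 5 at 1.18, and 13 to 20 at 1.33 (an SD ratio of 1.15) in most of the simulations. In the other direction the effect on type I error is small. With equal spread the planned model performs well and the alternative performs the same.

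These sizes rest on assumed variance ratios, an ICC range borrowed from parenting classes, 265 controls, and complete outcomes. They show what the model is exposed to, not what will happen in this trial. Nothing here makes the stated detectable effect wrong or the planned analysis invalid. It is a cheap improvement.

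**What to change.** In both the 24- and 36-month models:
- confine the random connector intercept to the intervention arm, keeping the eight unvisited families there as n=1 groups;
- estimate a separate residual variance for each arm;
- test the treatment coefficient with Satterthwaite or similar small-sample degrees of freedom;
- keep the common-variance n=1 model as a sensitivity analysis.

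The cost is one extra variance parameter, a sentence in section 2.4.1, a change to the mixed-model code, and a re-run on the simulated rehearsal data while masking holds. The same re-run should check that the imputation model lets BMI variance differ by arm.

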2.1. Trial design overview

NET-Works is a two-arm, randomized controlled trial to test the efficacy of a multi-setting, multi-component intervention approach to preventing obesity among racially/

ethnically diverse preschool age children. The NET-Works intervention includes four main components: 1) a pediatric primary care brief counseling intervention; 2) a home-based intervention delivered by NET-Works family connectors to support parents in making changes in the home environment and parenting practices to promote healthful eating and activity patterns; 3) community-based parenting classes designed to parallel the home-based intervention curriculum and provide social support to participating parents; and 4) linkages to neighborhood and community resources to support parents in promoting healthful eating and activity patterns for their children. Five hundred parent/child dyads will be randomized to either the NET-Works intervention or a usual care comparison condition and followed for three years. Participants will be assessed at baseline and annually. The primary hypothesis is that children randomized to the NET-Works intervention will have lower BMI at two and three years post-randomization relative to usual care comparison group children. BMI is the primary outcome across all four COPTR trials. Recruitment for the trial began in July 2012 and will be completed in December 2013, with the final three year follow-up data collected in December 2016.

2.2. Study setting and population

The target population for NET-Works is racially/ethnically diverse preschool children and their parent or primary caregiver. To reach the intended population, NET-Works has partnered with 12 primary care clinics and three managed health care systems that serve diverse populations with respect to race, ethnicity and income. Over 18 months, 500 families will be recruited, enrolled and randomized to the intervention or to the usual care comparison group. Administrative databases and centralized electronic scheduling systems at the partner clinics provide data needed to target recruitment efforts on two-to-four year old children residing in certain zip code areas. The clinics have recent data from preventive care visits available for calculation of child body mass index (BMI) percentile to focus recruitment efforts on children who are potentially BMI-eligible for the study.

2.3. Eligibility criteria and exclusions

Eligibility criteria are assessed on a telephone screening call and confirmed in person at the first data collection home visit. A child and his or her parent or primary caregiver are eligible for the study if: 1) the child is between ages of two and four years of age; 2) the child has no medical problems that would preclude study participation as determined by the primary care physician; 3) does not use any medications that would affect the child's growth; 4) the child's BMI is greater than or equal to the 50th percentile according to CDC age and sex reference standards with no upper limit [27]; 5) the family's income is below \$65,000 per year; 6) the child's parent agrees to participate in the study and does not plan to move out of the state in the next three years; 7) the parent or primary caregiver is willing and able to complete the evaluation measures and participate in intervention activities if assigned to the active intervention group; and 8) the parent or primary caregiver speaks either English or Spanish.

2.4. Recruitment

Recruitment procedures are adapted from those used in our previous pediatric primary care-based obesity prevention intervention trials. Administrative databases and centralized electronic scheduling systems at three partner health care organizations will provide data needed to target families of two–four year old children whose BMI percentile is at or above the 50th percentile for age and gender. Clinic liaisons obtain approval from each child's pediatrician to send a study invitation letter to the parent or primary caregiver. A list of physician-approved potentially eligible children is shared with the NET-Works recruitment team. NET-Works sends the parent or primary caregiver a study invitation letter from the pediatrician and researchers. Approximately five working days later, NET-Works recruitment staff follows up by phone to provide more information, asks additional screening questions, and assesses parent/primary caregiver's interest in the study. If the parent/primary caregiver is interested and the child appears to be eligible, a home visit for eligibility confirmation, consent, and data collection is scheduled. The purpose of this initial home visit is to: 1) explain and discuss the study, and begin to develop rapport with parents; 2) measure the index child's height and weight to confirm eligibility; 3) obtain informed consent; and 4) begin the process of collecting baseline data. Based on our pilot study experience we anticipate that the majority of the participating parent/caregivers will be female. We also anticipate recruiting a significant number of Hispanic families as well as non-Hispanic White, African American, and multi-race participants.

2.5. Randomization

Prior to the start of recruitment and enrollment, the study statistician created 6 blocked randomization schedules, one for each age group (2, 3, 4) by gender (M, F) stratum, that equally allocated children to the NET-Works intervention or the usual care comparison group in blocks of 10 to ensure equivalent study group size. Parent–child dyads will be randomized to treatment and control conditions after completion of all baseline measures, including data eligibility requirements established by the COPTR consortium. Data eligibility requirements include valid height and weight measurement, a minimum of one weekday and one weekend day NDS-R previous day dietary recall and four days of valid accelerometry data (see below for details regarding measurements). The study coordinator will randomly assign the participant to the condition shown in the next available slot in the stratum-appropriate pre-defined randomization schedule. The investigators and all assessment staff will remain blinded to experimental assignment until after the final follow-up assessments are completed.

